## Ethical Considerations

All consented participants will be part of the study. Written informed consents will be obtained from all study participants (parents or caregivers for children under the age of twelve) after thorough information on the study will be provided in the local language. Name of study participants will not be mentioned and incorporated in to the final dataset.

Medical services will be provided for volunteer study participants free of charge during the follow-up period. At all times, patient well-being will be given priority over his/her continuation in the study. In addition, round trip transport fare (100.00 Ethiopia Birr) will be provided for every patient every scheduled visit. The study protocol will be approved by Institute of Health Sciences Institutional Ethics Review Committee, Wallaga University and Ethiopian Public Health Institute Institutional Ethics Review Board.

## ANNEXES

## Annex 1. Patient Screening Form

## Patient Screening Form

STUDY SITE CODE: \_\_\_\_\_

TREATMENT GROUP: \_\_\_\_\_

1. Names:	2. Date: (dd/mm/yy) ____ / ____ / ____	3. Weight (kg):
4. Age*: years _____ months. _____	5. Gender: M _____ F _____	

1.	Patient aged > 6 months /Both sex	Yes:	No:
2.	P. vivax mono-infection asexual parasites/ $\mu$ l Pv 250-100,000/ $\mu$ l	Yes:	No:
3.	Body weight > 5 kg	Yes:	No:
4.	Patient with fever or history of fever in the previous 24 hours	Yes:	No:
5.	Non-pregnant or breast-feeding female	Yes:	No:
6.	Ability to swallow oral medication	Yes:	No:
7.	Residents living within 5 km radius of the health centre and agree to return for all scheduled follow up visits	Yes:	
8.	Willing to give informed consent	Yes:	No:
9.	Evidence of concomitant febrile illness If "YES", indicate illness. If "NO", leave blank. 
 
☐ Pneumonia/RTI      ☐ Measles
 
☐ Otitis Media      ☐ UTI
 
☐ Gastroenteritis      Other:
 
	Yes:	No:
10.	Evidence of severe malaria / danger signs If "YES" indicate criteria. If "NO", leave blank. 
 
☐ Unarousable coma (if after convulsion, > 30 min)
 
☐ Repeated convulsions (> 2 within 24 h)
 
☐ Recent convulsions (1-2 within 24 h)
 
☐ Altered consciousness(confusion, delerium,, coma)
 
	Yes:	No:

	
 
ə Lethargy
 
ə Unable to drink or breast feed
 
ə Vomiting everything
 
ə Unable to stand/sit due to weakness
 
ə Severe anaemia (Hb < 5.0 g/dL)
 
ə Respiratory distress (laboured breathing at rest)
 
ə Jaundice (yellow colouring of eyes)
 
		
11.	Known hypersensitivity to AL/CQ/DP	Yes:	No:

If any of the responses fall into the shaded area, exclude the patient from the study

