#### Exclusion Criteria

- ♣ Severe malaria with complication sign and symptoms (see Annex I)
- ♣ Signs or symptoms of severe malnutrition, defined as weight-for-age  $\leq$  3 standard deviations below the mean, symmetrical edema involving at least the feet, or mid-upper arm circumference <100 cm for children less than five years of age (NCHS/WHO normalized reference values; see Annex I)
- ♣ Mixed plasmodium infection
- ♣ Severe anemia, defined as hemoglobin (Hb) < 8 g/dl

- ♣ Presence of febrile conditions caused by diseases other than malaria (e.g. measles, acute lower respiratory tract infection, severe diarrhea with dehydration)
- ♣ Serious or chronic medical condition (e.g. cardiac, renal, hepatic diseases, sickle cell disease, HIV/AIDS)
- ♣ Positive pregnancy test or breastfeeding
- ♣ Unable or unwilling to take contraceptives for women of child-bearing age
- ♣ Children weighing less than 5 kilograms
- ♣ History of hypersensitivity reaction to any medication tested or used as an alternative treatment
- ♣ Participants with history of prolonged QT conditions
- ♣ Taking regular medication, which may interfere with antimalarial pharmacokinetics or efficacy (see Annex VII)?

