## **Treatment**

### **Antimalarial Treatment**

*P. vivax* patients will receive CQ+PQ. The correct drug doses will be determined by the dosing chart (Annex III). All drugs administered in the facility will be under supervision by the staff. Patients will be observed for 60 minutes after treatment for adverse reactions or vomiting. Those patients vomiting their medication within the first 30 minutes will receive a repeat full dose, while those vomiting from 30-60 minutes will receive half dose. Patients who vomit twice will be referred to higher level of care for management with parenteral artesunate therapy and withdrawn from the study. This is standard practice for anti-malarial treatment. All study drugs will be obtained from WHO Ethiopia office through Ethiopian Pharmaceutical Supply Agency.

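### The Annex 1 screening form does not match the Exclusion Criteria: it omits primaquine hypersensitivity, words breast-feeding ambiguously and has no line for five listed exclusions

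*Combined protocol and SAP*

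**What the plan says.** The Exclusion Criteria contain 12 entries. Those that matter most here are "Positive pregnancy test or breastfeeding", "History of hypersensitivity reaction to any medication tested or used as an alternative treatment", "Participants with history of prolonged QT conditions", "Serious or chronic medical condition" and "Unable or unwilling to take contraceptives for women of child-bearing age". The list also excludes severe malnutrition, regular medication that could interfere with the antimalarials, and haemoglobin below 8 g/dl.

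The Patient Screening Form in Annex 1 has 11 yes/no items and closes by telling staff to drop any patient with an answer in a shaded cell. Item 5 is "Non-pregnant or breast-feeding female". Item 11 is "Known hypersensitivity to AL/CQ/DP". Haemoglobin appears only inside item 10, as a sign of severe malaria, at below 5.0 g/dL.

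On treatment, the Antimalarial Treatment section says that *P. vivax* "patients will receive CQ+PQ", that is, chloroquine plus primaquine.

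**The concern.** Screening staff work from the form, and the form acts on its own answers. If it asks different questions from the criteria, the patients enrolled may differ from the patients the protocol means to enrol.

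Two things are at stake. The first is safety: several of the unmatched exclusions concern risk from the study drugs, and a patient who should have been excluded could receive them. The second is the analysed sample. The section on Patient Discontinuation or Protocol Violation withdraws patients who were included in error. Such a patient would be exposed to treatment and then contribute no outcome to the per-protocol estimate.

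**Working it through.** No sample-size or power figure enters this point. The check sets the 12 exclusions against the 11 form items and then looks for any other step that would catch what the form misses.

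| Exclusion | On the form | Other step before dosing |
|---|---|---|
| Severe malaria | Item 10 | Clinical evaluation at enrolment |
| Severe malnutrition | No line | Weight, arm circumference and oedema measured at screening |
| Mixed infection | Item 2 (mono-infection) | Species verified at enrolment |
| Haemoglobin below 8 g/dl | Only below 5.0 g/dL, within item 10 | Enrolment step excludes below 5 g/dL |
| Other febrile illness | Item 9 | Clinical evaluation at enrolment |
| Serious or chronic disease | No line | Baseline history might reveal it |
| Pregnancy or breast-feeding | Item 5, ambiguous | Urine test detects pregnancy only |
| Contraception | No line | No eligibility check described |
| Weight below 5 kg | Item 3 | Weighed at screening |
| Hypersensitivity | Item 11, AL/CQ/DP only | Baseline history might reveal it |
| Prolonged QT history | No line | Baseline history might reveal it |
| Interfering regular medication | No line | Baseline history might reveal it |

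**Count.** Four exclusions are on the form in matching substance (severe malaria, mixed infection, other febrile illness, low weight). Three are there in altered form (haemoglobin, breast-feeding, hypersensitivity). Five have no line. 4 + 3 + 5 = 12.

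**Item 5.** Read literally, the prefix governs only pregnancy, so a breast-feeding woman answers yes. A male patient literally answers no, which is also the answer of a woman who is pregnant and not breast-feeding. One yes/no line cannot separate these groups, whichever cell is shaded.

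**Item 11.** The criterion covers drugs tested and drugs used as alternatives. The tested drugs are chloroquine and primaquine, and only chloroquine is named. Elsewhere the protocol names parenteral artesunate (Antimalarial Treatment, Emergency Care) and oral quinine (Emergency Care) for patients who leave study treatment. Neither is on the form.

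**Haemoglobin.** The Exclusion Criteria use below 8 g/dl. Enrollment and Follow-up, step 3, uses below 5 g/dL. The form uses below 5.0 g/dL. A patient between 5 and 8 g/dl passes the form and the enrolment step but is excluded by the criteria. The passages contradict each other.

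**Other safeguards.** The Physical Examination section records a complete medical history at baseline, which it places before dosing on day 0. Body Weight and Screening step 4 provide the nutritional measurements. Enrollment and Follow-up adds the clinical evaluation, pregnancy test, species check and haemoglobin. The Day 0 list in Annex 8 adds no check on the missing items. None of these steps is said to ask about breast-feeding, primaquine hypersensitivity or QT history in order to decide eligibility.

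**The case against.** The strongest reply is that the form is not the only gate. The Exclusion Criteria still govern. The form's closing line makes a shaded answer sufficient to exclude, but does not say that a patient with no shaded answer is enrolled. A separate enrolment step with a clinician follows, and a complete history before dosing is where heart-rhythm conditions, chronic disease, drug reactions and regular medication would ordinarily come up. This largely stands, and it limits the claim to what could happen. It does not remove the gap, because the protocol never ties the history to an eligibility decision on these points.

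Several stronger readings are tempting and are not supported:

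- A reader might infer that the form will admit breast-feeding women. The intended meaning of item 5 may well be neither pregnant nor breast-feeding, and the shading that marks excluding answers is not visible in the text reviewed. Only the ambiguity is established.
- A reader might call AL and DP errors because they are not study drugs. The criterion extends to alternative treatments, and Rescue Treatment leaves the second-line drug to national guidelines, so their presence is not shown to be wrong. The omission of primaquine is.
- A reader might say malnutrition goes unchecked. It is measured at screening, and Body Weight links the screening weight to the nutrition criterion. What is missing is a line on the form recording the decision.
- A reader might treat the form's haemoglobin figure as a copying slip. It sits under severe malaria signs, and the direct conflict is between the Exclusion Criteria and the enrolment step.

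It can also be said that the sample has slack, since 73 is raised to 88 and the Kaplan-Meier analysis censors withdrawals. Censoring does keep partial information. The slack is thinner than it looks: at the plan's own 20% loss, 88 × 0.8 = 70.4, already below 73. That allowance is described as covering loss to follow-up and withdrawn consent, not patients included in error.

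**Conclusion.** The screening form contradicts the criteria it is meant to apply. Eight of the 12 exclusions are altered (three) or absent (five). The primaquine omission and the missing QT line are plain on the page and do not depend on how item 5 is read. As written, a patient whom the protocol excludes could pass screening, be dosed and then be withdrawn.

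The size cannot be put more precisely. The documents give no figures on how common these conditions are among the clinic's patients, and no rate of violations can be derived. Nor do they support saying that excluded patients will be enrolled, because the governing criteria and the baseline history remain in place.

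The conclusion assumes that the form is complete as shown. Its items run from 1 to 11 without a break to the closing instruction, which supports this. The standardized clinical form mentioned at enrolment cannot be checked in full, because parts of the annexed forms are broken in the text reviewed. If it carries the missing questions and is completed before dosing, the gap narrows, but Annex 1 would still disagree with the criteria.

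**What to change.** Align Annex 1 with the Exclusion Criteria before the form is used:

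- Split item 5 into one line for pregnancy and one for breast-feeding, each with a not-applicable option and the excluding answer clearly marked.
- Reword item 11 to name chloroquine, primaquine and whichever alternative treatments the sponsor confirms.
- Add one line each for prolonged QT history, serious or chronic disease, interfering regular medication, contraception and severe malnutrition.
- Reconcile the haemoglobin thresholds in the Exclusion Criteria (below 8 g/dl), Enrollment and Follow-up (below 5 g/dL) and Annex 1 (below 5.0 g/dL). The choice is a clinical one for the sponsor. The form should then carry the agreed figure as an eligibility line, distinct from the severe malaria signs.
- State in the protocol that the baseline history is reviewed against the exclusions before the first dose.

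The cost is a reprint, a few more questions per patient at screening and one added sentence in the protocol. The design, sample size and analysis do not change.

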## Annex 2. Enrolment Form

### Enrolment Form

STUDY SITE CODE: \_\_\_\_\_

TREATMENT GROUP: \_ \_\_\_\_\_

1. Age.....	2. Weight.....	3. Gender/Male.....Female.....
4. PIN/Study Number:.....	5. Number of tablets.....	6. Start Date: (dd/mm/yy)

7. Patients Full name:
8. Family head:
9. Mother's/Wife's (if married) name:
10. Caregiver's name and relationship:
11. Kebele/Street:
12. Home parish:
13 Village:
14. Home address and localising features/Owners name/Direction:
15. Phone number (s) and the owner(s):

3. Parasite asexual											
4. Gametocyte No											
5. Hemoglobin											
7. DBS/PCR											
8. Adverse events*	It is not drug related adverse event										
9. Concomitant treatment											
10. Reasons for withdrawal											
11. Remarks/ Rare Event	Complete Annex 27										
12. Treatment outcome											
Completed by (Initials)											

\*1. Headache 2. Anorexia 3. Nausea 4. Vomiting 5. Abdominal pain 6. Diarrhea 7. Cough 8. Behavioral change 9. Dizziness 10. Skin rash 11. Mouth ulcer 12. Joint pain 13. Weakness 14. Other specify \_\_\_\_\_

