## Rescue Treatment

Patients failing in any arm will be treated with second line drug per National Guidelines. Whereas, patients failing with the second line will be administered as of severe malaria criteria that is an indication of treatment failure.

The following are the known efficacy and adverse effects and pharmacokinetics of treatment drugs that will be used in the study:

**Chloroquine Plus Primaquine (CQ+PQ):** Chloroquine Plus Primaquine is a WHO Pre-qualified anti-malarial and FDA approved; WHO certifies the quality, safety and efficacy of the medication, and verifies that the manufacturer complies with WHO Good Manufacturing Practices. CQ+PQ is currently the first line anti-malarial recommended by Ethiopia FMOH for the treatment of uncomplicated falciparum infection. Adverse events are generally mild, most commonly GI (vomiting and diarrhea) and hematologic (anemia and eosinophilia). Its safety will be demonstrated in studies from Ethiopia and Uganda. Chloroquine has a half-life of 30-60 hours (53,54), while primaquine has a elimination half-life of 5-7 hours (54).

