#### **Safety endpoints**

The incidence of any adverse event will be documented. All patients will be asked routinely about previous symptoms and about symptoms that have emerged since the previous follow-up visit. When clinically indicated, patients will be evaluated and treated appropriately. All adverse events will be recorded on the case report form. Serious adverse events will be reported to all relevant authorities.

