### **Safety Assessment**

Safety will be assessed by recording the nature and incidence of adverse events and serious adverse events. Adverse events will be assessed by direct questioning. An adverse event is defined as any unfavourable, unintended sign, symptom, syndrome or disease that develops or worsens with the use of a medicinal product, regardless of whether it is related to the medicinal product. All adverse events must be recorded on the case report form. A serious adverse event is defined as any untoward medical occurrence that at any dose:

- results in death, is life threatening
- requires hospitalization or prolongation of hospitalization
- results in a persistent or significant disability or incapacity
- Is a congenital anomaly or birth defect.

‘Life-threatening’ means that the person will be at immediate risk for death; it does not refer to an adverse event that might have caused death if it were more severe. ‘Persistent or significant disability or incapacity’ means that a person’s ability to carry out normal life functions is substantially disrupted. All serious adverse events occurring during the study must be recorded and reported by the principal investigator to the sponsor, regardless of whether the principal investigator considers the events to be related to the investigated medicine. The investigator will collect information on all people who become pregnant while participating in this study and will record the information on the appropriate form. The person will also be followed to determine the outcome of the pregnancy.

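### The adverse-event row of the visit form carries fixed non-relatedness text that conflicts with the rule to record every adverse event whatever its relation to the drug

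*Combined protocol and SAP*

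**What the plan says.** The visit case report form stands among the annexes, between the enrolment form (Annex 2) and the outcome classification (Annex 4). Its row 8, for adverse events, contains the words "It is not drug related adverse event". A footnote to the row gives 14 codes, 13 named symptoms and an open category. The list begins "Headache 2. Anorexia 3. Nausea 4. Vomiting 5. Abdominal pain 6. Diarrhea". Row 11, for remarks and rare events, holds a short instruction in the same cell position: "Complete Annex 27".

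The body of the protocol sets these rules:

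- Safety endpoints: "The incidence of any adverse event will be documented", and "All adverse events will be recorded on the case report form".
- Safety Assessment: an adverse event counts "regardless of whether it is related to the medicinal product", and "All adverse events must be recorded on the case report form".
- Rescue Treatment, on the study drugs: "Adverse events are generally mild, most commonly GI (vomiting and diarrhea) and hematologic (anemia and eosinophilia".
- Annex 9 (follow-up schedule): drug adverse-event monitoring is marked in every column, day 0 included.

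**The concern.** The case report form is where the safety endpoint is measured, and staff will follow what is printed in the row they fill in. Fixed text denying a drug relation can be taken in two ways: as a rule about which events to enter, or as a statement about the events entered. The first could keep drug-related events off the form. The second settles causality before anyone has assessed it.

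Section Enrollment and Follow-up (step 4) gives every *P. vivax* participant chloroquine plus primaquine, so no untreated group can show which events are due to the drugs. Any later statement on attribution would rest on timing and on judgement of each event, and a pre-printed answer replaces that judgement.

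**Working it through.** The plan gives no figure on this point and no event rate. The check therefore sets the form beside the rules and works out what each reading does to the endpoint.

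**1. Column scope.** Row 8 has 11 cells after its label, matching the 11 columns of Annex 9 (day 0 to any other day). The text falls in the first cell. That fits a note for day 0 only. It also fits text meant for the whole row, because the row 11 instruction falls in the same cell and has no evident reason to apply to day 0 alone. The form's visit headings are not in the available text, so the scope stays open.

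**2. Whole row.** Among all patients, let *a* be the share with at least one event judged unrelated, and *b* the share whose only events are judged related. The endpoint, incidence of any adverse event, is *a* + *b*.

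| How staff read the text | Any-event incidence recorded | Shortfall | Effect on relatedness |
|---|---|---|---|
| Enter only unrelated events | *a* | (*a* + *b*) − *a* = *b* | related events absent |
| Label on whatever is entered | *a* + *b* | 0 | every event marked unrelated, unassessed |

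The first reading breaks the record-all rule in both safety sections. The second leaves the planned endpoint intact but is at odds with a definition that leaves causality open. The documents give neither *a* nor *b*. The shortfall under the first reading can lie anywhere from 0 to the full incidence *a* + *b*.

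**3. Day 0 only.** Section Enrollment and Follow-up (step 5) gives the first dose on day 0 under observation. Section Antimalarial Treatment has patients watched for 60 minutes afterwards for adverse reactions or vomiting. Annex 9 marks drug adverse-event monitoring that day. Events after the dose can therefore arise on day 0, and the two readings in step 2 apply to them. Symptoms present before the dose, and not worsening after it, fall outside the protocol's definition, which requires that an event develop or worsen with use of the product.

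**4. Are drug effects among the codes?** Vomiting (code 4) and diarrhoea (code 6) are named in Rescue Treatment as common with the study drugs. Skin rash is code 10, and Emergency Care treats a raised rash as suggesting a severe allergic reaction. So the row is meant to hold events that may well be drug related.

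**The case against.** The best defence is that this is a baseline remark. The text sits in what would be the day 0 cell, and symptoms before dosing cannot be caused by the drug. The row also needs open cells for its codes, so text spanning the whole row would leave nowhere to write. The row 11 comparison is weaker than it looks, because that row only sends staff to another form. This stands as far as scope goes: a day 0 note cannot be ruled out. It does not remove the conflict, since day 0 also includes the dose and the observation after it, and nothing visible limits the note to the period before dosing.

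A second defence is that the author meant events that are not only drug related, which would agree with the definition. The form does not say so.

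A third is that staff would not omit related events, because the row's own codes include known drug effects and two sections say to record everything. That makes omission less likely, but the contradiction still reaches whoever fills in the form.

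A reader might infer more than the documents support:

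- *That the study will report a related-event incidence biased towards zero.* No such report is planned. The endpoint ignores relatedness, and the Statistical Analysis section names no adverse-event analysis.
- *That anaemia would be lost.* Anaemia is not a named code in row 8. Haemoglobin has its own row, is measured on days 0, 14, 28 and 42, and has its own paired tests.
- *That the form has no place for relatedness.* Row 6 and the form to which row 11 refers are not in the available text, so this cannot be established.

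**Conclusion.** The conflict is real and limited. Whether the row 8 text covers the whole row or only day 0, it disagrees with the rule to record all adverse events regardless of relation to the drug. Only the reading that restricts entries to unrelated events biases the stated endpoint. It does so downwards, by the share of patients whose only events (or, if the scope is day 0, whose only events on that day) are judged related. The labelling reading leaves any-event incidence unchanged and affects only what can later be said about causality.

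The conclusion assumes that the text is part of the blank form, as its position beside the row 11 instruction suggests, and that staff act on what is printed. Serious events have a separate reporting duty regardless of relatedness, and vomiting after a dose is also picked up by the observation and withdrawal rules, so row 8 is not the only route for those events. Sample size and the primary efficacy estimate are untouched.

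**What to change.** Delete the text from row 8, or replace it with wording that matches the Safety Assessment definition, for example: *record every adverse event, whether or not related to the study drug*. If a baseline note was intended, give symptoms before dosing their own line, so that they are kept apart from events after the first dose.

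If the investigators want to report relatedness, record it for each event by investigator judgement and not by pre-printed text. Further fields for severity or seriousness, or a second incidence table, would be a matter of preference and are not needed to remove the conflict.

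The cost is one line changed on the form before first use, with no effect on visits, sample size or analysis. If forms are already in use, ask staff how they read the row and note the answer with the safety results.

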## **Annex 10: Consent Procedure**

### **Categories of consent forms**

- I. for children **6 months-11 years** old parental/guardian permission will be obtained
- II. For patients **12 -17 years old** assent from the patient and parental/guardian permission will be obtained
- III. For patients age **18 yrs. and older** adult consent will be obtained

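### Anaemia is named as a common CQ+PQ event and haemoglobin is measured on four days, but no rule turns a haemoglobin value into a counted adverse event

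*Combined protocol and SAP*

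**What the plan says.** - The drug description under Rescue Treatment says of CQ+PQ: "Adverse events are generally mild, most commonly GI (vomiting and diarrhea) and hematologic (anemia and eosinophilia".
- Safety endpoints: "The incidence of any adverse event will be documented".
- Safety Assessment: "Adverse events will be assessed by direct questioning". It also requires every adverse event to be entered on the case report form, whether or not it is related to the drug.
- The follow-up record form, printed between Annex 2 and Annex 4, has an adverse-event row whose codes are "1. Headache 2. Anorexia 3. Nausea 4. Vomiting 5. Abdominal pain 6. Diarrhea 7. Cough" and then "8. Behavioral change 9. Dizziness 10. Skin rash 11. Mouth ulcer 12. Joint pain 13. Weakness 14. Other specify". Haemoglobin has a separate row on the same form.
- Laboratory Examination, Annex 8 and Annex 9 schedule haemoglobin for all patients on days 0, 14, 28 and 42. Annex 8 allows it on other days if clinically indicated.
- Statistical Analysis plans t-tests on mean haemoglobin: paired between days, and between two parasitaemia groups on each of the four days. It gives no incidence or grade of anaemia.
- Exclusion Criteria exclude haemoglobin below 8 g/dl. Enrollment and Follow-up excludes only haemoglobin below 5 g/dl.

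**The concern.** Anaemia is a laboratory finding. A patient asked about symptoms may report weakness or dizziness, or nothing, while the haemoglobin row of the same form shows a clear fall. Unless a rule carries that value into the adverse-event row, whether it is counted depends on the individual clinician.

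The safety result at stake is the incidence of an event that the protocol itself expects to be common. If the adverse-event table shows few or no cases of anaemia, readers will take that as evidence of haematological safety. With 0 cases in 88 patients, for example, the one-sided 95% upper bound is 1 − 0.05^(1/88) = 3.3%. That bound is valid only if every case would have been recorded.

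**Working it through.** The plan states no figure on this point, so the check is mainly a comparison of sections.

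**1. Named effects against form codes**

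| Effect named under Rescue Treatment | Code on the form | Measured by a scheduled test |
|---|---|---|
| Vomiting | 4 | not applicable |
| Diarrhoea | 6 | not applicable |
| Anaemia | none | yes, haemoglobin on days 0, 14, 28, 42 |
| Eosinophilia | none | no differential count scheduled |

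Two of the four named effects have a code. Neither blood effect does.

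**2. Routes from a haemoglobin value to the incidence**

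- Patient report: only if the anaemia causes a symptom. It would then probably be coded as that symptom, for example weakness (13) or dizziness (9).
- Code 14, open text: possible, but only if the clinician decides that the value is an event. No threshold guides that decision.
- Analysis of the haemoglobin row: possible from the data, but not planned as an incidence.

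**3. What the planned haemoglobin analyses show**

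There are five paired comparisons (days 0–14, 0–28, 14–28, 0–42, 28–42) and four between-group comparisons (one per day), 5 + 4 = 9, all of means. The general descriptive statistics include a range. Applied to haemoglobin, that would show the lowest value on a day, but not how many patients were low or had fallen.

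A mean can hide a few large falls. As an illustration, assume a fall of 3 g/dl (the gap between the two exclusion limits, 8 − 5) in k of 88 patients:

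| k | Change in the mean | Average rise in the others that cancels it |
|---|---|---|
| 2 | 2 × 3 / 88 = 0.07 g/dl | 6 / 86 = 0.07 g/dl |
| 4 | 4 × 3 / 88 = 0.14 g/dl | 12 / 84 = 0.14 g/dl |
| 9 | 9 × 3 / 88 = 0.31 g/dl | 27 / 79 = 0.34 g/dl |

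**4. Possible shortfall**

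Inputs: N = 88 (Sample Size Determination); true rate p and capture proportion c are both assumed. Shortfall = N × p × (1 − c).

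| p (assumed) | Expected cases, 88 × p | Shortfall, c = 100% | c = 50% | c = 0% |
|---|---|---|---|---|
| 2% | 1.8 | 0 | 0.9 | 1.8 |
| 5% | 4.4 | 0 | 2.2 | 4.4 |
| 10% | 8.8 | 0 | 4.4 | 8.8 |

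The documents fix neither p nor c, so the table shows a range and is not an estimate.

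**5. Why the baseline limit matters**

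If nobody below 8 g/dl is enrolled, any later value below 8 is new. If only values below 5 g/dl are excluded, patients between 5 and 8 may be enrolled, and a count of values below 8 after day 0 would include patients who started there. A count of new events needs a settled baseline rule.

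**The case against.** The strongest reply is that nothing prevents recording. Code 14 accepts any event, all events must be entered, and the data-handling section provides for coding open-ended diagnoses. The form's list is a set of recording codes; no section makes it the interview script. Every visit has a physical examination and a check for danger signs, and the screening form lists jaundice among those signs. Haemoglobin is held for every attending patient, so an incidence of anaemia can be derived whatever the code list says. The Rescue Treatment paragraph also calls CQ+PQ first line for falciparum malaria, so its list of effects may be carried over from another protocol.

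Most of this stands, and it limits the point. A reader might infer that the incidence is bound to be too low; the documents do not show that, since at full capture the shortfall is zero. What survives is narrower. Permission to record is not a rule to record, coding of open text cannot recover what was never entered, and a derived incidence is possible but not planned.

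Two further readings are tempting and do not hold:

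- The form's rare-event row says "Complete Annex 27", while the last annex in the available text is "Annex 10: Consent Procedure". A reader might infer that blood events are lost through this reference. The row is for rare events and the protocol calls the blood effects common, so the reference cannot lower their count. It looks like a clerical slip.
- A reader might infer that adding an eosinophilia code would help. With no differential count scheduled, a code alone would change nothing.

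**Conclusion.** The point holds as a gap in the analysis plan. Anaemia is named as common, it is measured on four days, and it has neither a form code nor a rule that makes it an adverse event. The incidence promised as the safety endpoint may therefore omit anaemia that patients do not report.

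The size cannot be computed from the documents. A reader might infer a firm figure, such as the chance of recording no case among 88 rising from 0.95^88 = 1.1% to 0.975^88 = 10.8%. That takes a 5% true rate and 50% capture, both assumed, so it cannot stand as a finding.

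The conclusion rests on the Rescue Treatment list being meant for this drug pair. It is a minor point, but one that changes a reported safety result at almost no cost.

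**What to change.** 1. **Reconcile the limits first.** Exclusion Criteria (<8 g/dl) and Enrollment and Follow-up (<5 g/dl) must be brought into agreement. Which is right is for the investigators.
2. **Derive anaemia as an adverse event.** Prespecify one haemoglobin limit. From the day 0, 14, 28 and 42 values, report the number and proportion of patients newly below it after day 0, with an exact 95% CI. The denominator is patients not below the limit on day 0 who have at least one later value; state how many have none.
3. **Show individual change.** Report the distribution of each patient's largest fall from day 0, alongside the planned mean comparisons.
4. **State the limits of the data.** No haemoglobin is scheduled between day 0 and day 14, so a fall that recovers by day 14 is seen only if an unscheduled value was taken. State that eosinophilia is not assessed because no differential count is scheduled.
5. **Optional form edit.** Add codes for anaemia, dark urine, jaundice and pallor.

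Two separate clerical checks can go into the same revision: the annex reference in the rare-event row, and the printed words "It is not drug related adverse event" in the adverse-event row, which conflict with a definition that disregards relatedness. The point above depends on neither.

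Cost: a few sentences in Statistical Analysis, one eligibility correction and, if wanted, a revised form footnote. No new test, visit or patient is needed. The reported adverse-event incidence may rise.
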